11.1.9. Suspected Unexpected Serious Adverse Reactions

An AE is considered a suspected unexpected serious adverse reaction (SUSAR) if the nature or severity is not consistent with the applicable product Reference Safety Information (RSI). For dasiglucagon, the expectedness of an AE will be determined by whether or not it is listed in the RSI section of the investigator's brochure.

11.2. Collection, Recording, and Reporting of Adverse Events

All AEs, whether serious or non-serious, will be reported from the time a signed and dated ICF is obtained until the end of the posttreatment follow-up period (which may include contacts for follow-up of safety) or inclusion in the ZP4207-17106 trial. Parent(s)/guardian will be asked about their child's condition by open questioning, such as "How has your child been feeling since you were last asked?" at each contact with the trial site (visit or telephone). Parent(s)/guardian will also be encouraged to spontaneously report AEs occurring at any other time during the trial. In addition, patients will be observed for any signs or symptoms.

All AEs, regardless of seriousness, severity, or presumed relationship to the trial drug, must be recorded and evaluated by the investigator. Whenever possible, diagnoses should be given when signs and symptoms are due to a common etiology. If no diagnosis can be made, the investigator should record each sign and symptom as individual AEs. Investigators must record their opinion concerning the relationship of the AE to the trial drug. All measures required for AE management must be recorded in the source document and reported according to sponsor instructions.

Each AE must be reported on the AE eCRF within 5 calendar days of the investigator becoming aware of the event.

All AE information should at a minimum include the following:

- Date and time of onset
- Date and time of investigator's first information about the AE
- Seriousness
- Severity
- Causal relationship with trial product
- Measures taken due to AE
- Interruption or discontinuation of treatment with trial product
- Date and time of resolution and final outcome

Each AE will be coded using the latest version of the Medical Dictionary for Regulatory Activities (MedDRA).

All SAEs, including those spontaneously reported to the investigator within 30 days after the last dose of trial drug, must be reported within 24 hours after obtaining knowledge about the event, by completing the SAE form in EDC. A separate SAE form should be completed for each SAE.

All SAEs will be reported in EDC; for each reported event, a system-generated e-mail will be sent to the Safety CRO (), medical monitor, sponsor's medical director, and trial manager.

Specific information about AESIs will be collected via the SAE form (if qualifying for an SAE), as well as via dedicated AESI eCRF page(s). Reporting requirements for serious and non-serious AEs as described previously also apply for serious and non-serious AESIs.

Other important events (Section 11.1.6) will be reported via a dedicated eCRF page. Reporting timelines will be within 24 hours if related to an SAE and 5 calendar days for all other events.

It is the responsibility of to report all SUSARs that occur in this trial to competent authorities, the institutional review board (IRB), or independent ethics committee (IEC) in accordance with the local requirements in force and ICH guideline for GCP.

11.2.1. Contact Information

Pharmacovigilance for this trial is outsourced to great trial; refer to Appendix A for contact details.

11.3. Follow-up of Adverse Events

The investigator must record follow-up information in the eCRF. Follow-up questions to investigators regarding serious adverse events are queried directly by to the investigator.

Follow-up information must be reported according to the following:

• SAEs: All SAEs must be followed until the outcome of the events is "recovered/resolved," "recovered/resolved with sequelae," or "fatal," and until all queries have been resolved. Cases of chronic conditions, cancer, or AEs that are ongoing at time of death (where death is due to another AE) may be closed with the outcome "recovering/resolving" or "not recovered/not resolved." Cases can be closed with the outcome of "recovering/resolving" when the patient has completed the follow-up period and is expected by the investigator to recover

The SAE follow-up information should only include new (e.g., corrections or additions) information and must be reported **within 24 hours** of the investigator's first knowledge of the information. This is also the case for previously non-serious AEs which subsequently become SAEs.

• Non-serious AEs: Non-serious AEs must be followed until the outcome of the event is "recovering/resolving," "recovered/resolved," or "recovered/resolved with sequelae" or until the end of the follow-up period stated in the protocol, whichever comes first, and until all queries related to these AEs have been resolved. Cases of chronic conditions, cancer, or AEs that are ongoing at time of death (where death is due to another AE) may be closed with the outcome of "recovering/resolving" or "not recovered/not resolved." Cases can be closed with the outcome of "recovering/resolving" when a patient has completed the follow-up period and is expected by the investigator to recover

If a potential hypersensitivity reaction is observed, additional blood samples, as clinically indicated, may be required to further characterize the potential hypersensitivity reaction. If an anaphylactic shock is suspected, samples may be taken for the measurement of tryptase. In this case, a blood sample should be taken 3-4 hours after the event and again approximately 1-2 weeks later to determine tryptase baseline levels. In addition, assessments for elevated histamine levels may be considered.

The investigator must ensure that the worst-case severity and seriousness of an event is kept throughout the trial, from the start of trial product administration (i.e., the most severe of the applied severity/seriousness categories should be ascribed to the event). Accordingly, for AEs with onset after trial product administration, changes in the severity or seriousness of an event should not lead to reporting of separate AEs. In contrast, for AEs with onset before trial product administration, any worsening of severity/seriousness after trial product administration should be recorded as a separate AE, with onset date of the event corresponding to the date of the severity/seriousness upgrade.

If an AE is resolved and re-appears later then it should be reported as a new AE. Queries or follow-up requests must be responded within 14 calendar days from the date of receipt of the request, unless otherwise specified in the follow-up request.

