9.2. Treatments Administered

In Treatment Period 1, patients will receive SOC only or SOC plus dasiglucagon for 4 weeks based on their treatment assignment. In Treatment Period 2, all patients will receive SOC plus dasiglucagon for 4 weeks.

Dosing of dasiglucagon will approximate continuous infusion by delivering small doses at frequent intervals via the infusion pump.

The pump administers $0.000025 \text{ mL/dose} \sim 0.1 \mu\text{g/dose}$ (4 mg/mL formulation):

- $10 \mu g/hour \sim 0.5 \mu g every 3 min$
- $20 \mu g/hour \sim 1 \mu g every 3 min$
- $30 \mu g/hour \sim 1.5 \mu g every 3 min$
- $40 \mu g/hour \sim 2 \mu g every 3 min$
- 50 μ g/hour ~ 2.5 μ g every 3 min
- $60 \mu g/hour \sim 3 \mu g every 3 min$
- $70 \mu g/hour \sim 3.5 \mu g every 3 min$

Plasma glucose assessments will be performed regularly (at least 3 times daily, preferably before main meals, and as instructed by the investigator) throughout the trial to guide adjustments to the gastric dextrose infusion and/or trial drug product upon the investigator's discretion.

Dasiglucagon treatment will be initiated at 10 μ g/hr (t=0). Every 2 hours (t=2, 4, 6, etc.), the dose will be increased by an additional 10 μ g/hr until either:

- 1. The patient is weaned off entirely from gastric dextrose infusion and/or glucose-fortified feeds, or
- 2. Plasma glucose during the last 2 hours was consistently above 120 mg/dL (6.7 mmol/L), or
- 3. The maximum trial drug product infusion rate of 70 μg/hr is reached, or
- 4. Adverse events emerge that are considered to be related to dasiglucagon (e.g., nausea and vomiting) and limit further dose escalation

The dose of dasiglucagon should not be escalated beyond reaching the treatment objectives of PG in the range of 70-120 mg/dL (3.9-6.7 mmol/L) while approaching a normal feeding regimen according to age.

The 2-hour dose-adjustment interval will allow plasma drug levels to approach approximately steady-state before the dose is further increased. The maximum dose of trial drug product that can be administered over the first 24 hours is shown in Table 1. The maximum cumulative dose over the first 24 hours is 1.26 mg.

After the first 24 hours, the dose of dasiglucagon can still be modified to optimize each patient's treatment and to reduce gastric dextrose infusions. The maximum dose of dasiglucagon will be 70 µg/hr, corresponding to a maximum of 1.68 mg per day.

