9.5. Method of Assigning Patients to Treatment Groups

In Treatment Period 1, patients will be randomly assigned in a 1:1 ratio to receive either SOC only or SOC plus dasiglucagon for 4 weeks using a block randomization scheme stratified by region US/non-US). In Treatment Period 2, all patients will receive SOC plus dasiglucagon for 4 weeks. The stratification by region addresses the difference in practice of treatment for CHI, especially the prominent difference in frequency of sub-total pancreatectomy for diffuse CHI between US/non-US.

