6.1.7. Derived Variables

- **Day 1** = first day of Treatment Period 1, where either dasiglucagon is first initiated (dasiglucagon + SOC treatment group) or date of randomization (SOC only treatment group). Study day will be calculated with respect to Day 1.
- **Study Week** = a 7- or 21-day period derived for displays of events related to CGM and/or SMPG results, gastric carbohydrate administrations, health care outcomes, and other assessments that may occur between clinic visits where a defined study week is needed. The study weeks will be derived as follows:

Study Week	Planned Days	Analysis Start Date	Analysis Stop Date
Baseline	Days -14 – -1	Analysis Stop Date – 13 days	Day 1 visit date – 1 day
Week 1 *	Days 1 – 7	Day 1 visit date	Week 5 visit date – 22 days
Week 2	Days 8 – 14	Analysis Stop Date – 6 days	Week 5 visit date – 15 days
Week 3	Day 15 – 21	Analysis Stop Date – 6 days	Week 5 visit date – 8 days
Week 4	Days 22 – 28	Analysis Stop Date – 6 days	Week 5 visit date – 1 day
Weeks 2-4	Days 8 – 28	Same as Week 2 Analysis Start Date	Week 5 visit date – 1 day
Week 5 *	Days 29 – 35	Week 5 visit date	Week 9 visit date – 22 days
Week 6	Days 36 – 42	Analysis Stop Date – 6 days	Week 9 visit date – 15 days
Week 7	Days 43 – 49	Analysis Stop Date – 6 days	Week 9 visit date – 8 days
Week 8	Days 50 – 56	Analysis Stop Date – 6 days	Week 9 visit date – 1 day
Weeks 6-8	Days 36 – 56	Same as Week 6 Analysis Start Date	Week 9 visit date – 1 day

Study Week	Planned Days	Analysis Start Date	Analysis Stop Date
------------	--------------	---------------------	--------------------

* This might end up being more or less than 7 days if the Week 5 visit day is not exactly at Day 29 or if the Week 9 visit day is not exactly at Day 57; both Week 5 and Week 9 visits have a \pm 2 day visit window.

No overlap in days between study weeks is allowed, except in cases where a multiple-week period is indicated. If there is overlap, the earlier week is favored. In case of early termination before a subject reached the end of the respective period (Week 5 or Week 9), the derivation for the weeks will be based on the planned day up to date of discontinuation (where any week after date of discontinuation will be set to missing), as follows:

Study Week	Planned Days	Analysis Start Date	Analysis Stop Date
If subject discontinues trial before reaching Week 5:			
Week 1	Days 1 – 7	Day 1 date	Earliest of Analysis Start Date + 6 days, or date of trial discontinuation

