If subject discontinues trial before reaching Week 9:			
Week 2	Days 8 – 14	Date 1 date + 7 days	Earliest of Analysis Start Date + 6 days, or date of trial discontinuation
Week 3	Day 15 – 21	Date 1 date + 14 days	Earliest of Analysis Start Date + 6 days, or date of trial discontinuation
Week 4	Days 22 – 28	Date 1 date + 21 days	Earliest of Analysis Start Date + 6 days, or date of trial discontinuation
Weeks 2-4	Days 8 – 28	Same as Week 2 Analysis Start Date	Same as latest of Week 2, Week 3, or Week 4 Analysis Stop Date
Week 5	Days 29 – 35	Week 5 date	Earliest of Analysis Start Date + 6 days, or date of trial discontinuation
Week 6	Days 36 – 42	Week 5 date + 7 days	Earliest of Analysis Start Date + 6 days, or date of trial discontinuation

Study Week	Planned Days	Analysis Start Date	Analysis Stop Date
Week 7	Days 43 – 49	Week 5 date + 14 days	Earliest of Analysis Start Date + 6 days, or date of trial discontinuation
Week 8	Days 50 – 56	Week 5 date + 21 days	Earliest of Analysis Start Date + 6 days, or date of trial discontinuation
Weeks 6-8	Days 36 – 56	Same as Week 6 Analysis Start Date	Same as latest of Week 6, Week 7, or Week 8 Analysis Stop Date

- **Study Visit** = in-clinic visit as per the schedule of events, to be used for assessments that can only occur during a clinic visits (e.g., PedsQL, safety assessments like clinical laboratory assessments and vital signs).
- **Change from baseline** = value at current time point – value at baseline.
- **TEAE** = an AE with an onset at the time of or following the start of treatment with the trial drug (dasiglucagon + SOC arm) or date/time of randomization (SOC only arm) through the Follow-up visit or Early Termination visit, whichever occurs first.
- **PK Clearance:**

$$CL/f \text{ (L/h)} = R_0/C_{ss}$$

where R_0 = infusion rate (pmol/h) and C_{ss} = concentration at steady state (pmol/L), weight ($1\mu\text{g/kg/hr} = 295.7 \text{ nmol/kg/h}$)

- **SMPG-detected Hypoglycemia episode** = PG <70 mg/dL or 3.9 mmol/L, as detected by SMPG and reported in the eCRF. A single hypoglycemia episode is defined as up until 60 minutes from the start of the episode even if normoglycemia (>70 mg/dL) is not reached within this time. A new episode of hypoglycemia is to be reported when the next PG value below 70 mg/dL (3.9 mmol/L) is measured. Episodes are defined as the ones entered in the eCRF, no statistical programming will be done to define an episode.

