9.1. Adverse Events

An AE is any untoward medical occurrence in a clinical trial patient administered a medicinal (investigational or non-investigational) product and which does not necessarily have a causal relationship with this treatment. An AE can therefore be any unfavorable and unintended sign (including an abnormal laboratory finding), symptom, or disease temporally associated with the use of a product, whether or not related to the product. Adverse events that begin after the first dose of dasiglucagon (dasiglucagon + SOC treatment group) or randomization (SOC only treatment group) will be defined as treatment emergent (TEAE).

The causal relationship of the AE to the study drug is determined by the investigator as Not Related, Unlikely, Possible, and Probable. These will be mapped to Unrelated (*Not Related* or *Unlikely*) and Related (*Possible* or *Probable*) for summarization purposes. Relationship for patients on SOC only is expected to be “Not related” according to data entry guidelines. If it is missing for a patient in this period it should be mapped to “Not related” other missing data will be mapped to “Related”.

Adverse event severity grades are reported as mild, moderate, or severe.

Each patient will be counted only once within each summation level system organ class (SOC) and preferred term (PT). If a patient experiences more than 1 TEAE within each summation level only, the TEAE with the strongest relationship or the maximum severity, as appropriate, will be

included in the summaries of relationship and severity. The summary will be presented in descending order of frequency of SOC and then PT within SOC based on dasiglucagon arm of period 1, then by standard of care only in period 1 and then by period 2.

The incidence of TEAEs will be summarized with frequencies and percentages for patients in Safety Set (including number of TEAEs occurring, as well as rate of events), by treatment group within treatment period and the following:

- SOC and PT
- SOC, PT, and severity
- SOC, PT, and relationship to study drug
- SAEs by SOC and PT

Rate of events will be described as Exposure-adjusted TEAE rate calculated by summing all events and dividing by total exposure time. For Standard of Care only the total exposure time will be calculated from randomization to day before first intake in treatment period 2.

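### Because the worst-severity recording rule starts at first dasiglucagon dose, a Period 1 adverse event that worsens after Week 5 is recorded differently by arm, which can tilt the Period 1 severity and SAE tables against dasiglucagon

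*Protocol*

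**What the plan says.** Protocol 11.3, repeated in German 12.3, requires that the "worst-case severity and seriousness of an event is kept throughout the trial, from the start of trial product administration". It then gives two cases. After trial product has started, "for AEs with onset after trial product administration, changes in the severity or seriousness of an event should not lead to reporting of separate AEs". By contrast, "for AEs with onset before trial product administration, any worsening of severity/seriousness after trial product administration should be recorded as a separate AE". That new AE is dated at the upgrade.

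Trial product is dasiglucagon. In Treatment Period 1 patients are "randomly assigned in a 1:1 ratio to receive either SOC only or SOC plus dasiglucagon for 4 weeks" (Protocol 9.5). Then "In Treatment Period 2, all patients will receive SOC plus dasiglucagon for 4 weeks" (Protocol 9.2).

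The SAP uses a different anchor. In SAP 6.1.7, Day 1 is when "either dasiglucagon is first initiated (dasiglucagon + SOC treatment group) or date of randomization (SOC only treatment group"). The TEAE window runs from first dose on dasiglucagon, or from "date/time of randomization (SOC only arm) through the Follow-up visit or Early Termination visit, whichever occurs first". SAP 9.1 summarizes TEAEs, including by severity and as SAEs, "by treatment group within treatment period and the following" classifications, and counts each patient once per level at maximum severity.

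**The concern.** The same recording rule starts about four weeks apart in the two arms. The SAP recognised that SOC patients have no first dose in Period 1 and moved their TEAE start to randomization. The rule that decides which grade an AE record carries, and whether a worsening is a new record, stayed at first dose.

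Period 1 is the only randomized, concurrent safety comparison, because everyone receives dasiglucagon in Period 2. If severity reached in later weeks can flow back into the Period 1 column of one arm only, the severity and SAE tables for that period can differ by arm even when the drug has no effect on AEs.

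**Working it through.** There is no stated figure to reproduce. The check applies the rule to the same event in each arm and then illustrates the size.

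**1. Same event, both arms** (Protocol 11.3)

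| Event | Dasiglucagon from Day 1 | SOC only until about Day 29 |
|---|---|---|
| Starts mild in Week 3, severe or serious in Week 6 | One record, Period 1 onset, severe or serious | Period 1 record stays mild; new AE with Period 2 onset |
| Starts between consent and Day 1, worsens in Weeks 1-4 | New AE dated at the upgrade, hence a TEAE | Section 11.3 calls for no new record |
| Resolves, then recurs | New AE | New AE |

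The first row is the main path. It changes the grade or seriousness of an existing Period 1 record and adds no Period 1 record. The second row is a secondary path. It could change Period 1 counts, but for SOC it rests on what 11.3 leaves unsaid.

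**2. What the SAP does with these records.** SAP 9.1 takes maximum severity and has no rule limiting it to the grade reached within the period. Allocation of an AE to a period by onset is not stated. It is implied by the onset-based TEAE definition and by SOC exposure closing the day before first intake in Period 2. On that reading, a Period 1-onset AE can be upgraded until as late as Day 85 on dasiglucagon (about Day 57 if the patient enters the extension), but only until about Day 28 on SOC.

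**3. Size, main path.** The documents give no AE rate, no share of AEs ongoing at Day 29 and no rate of worsening, so every input here is assumed. With the same AE process in both arms:

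excess share of upgraded Period 1 AEs = P(ongoing at Day 29) × P(worsens later, given ongoing)

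- 5% and 5%: 0.05 × 0.05 = 0.0025, or 0.25 points
- 20% and 20%: 0.20 × 0.20 = 0.04, or 4 points
- 30% and 30%: 0.30 × 0.30 = 0.09, or 9 points

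If each of 16 patients per arm had 3 AEs (16 × 3 = 48), the first two cases give 48 × 0.0025 = 0.12 and 48 × 0.04 = 1.92 AEs shown at a worse grade on dasiglucagon and none on SOC.

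A simulation with onset uniform over Days 1-28, exponential duration, constant daily worsening hazard and follow-up to Day 85 gives these shares of Period 1-onset AEs upgraded (dasiglucagon vs SOC):

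| Mean duration | Hazard 0.01/day | Gap (points) | Hazard 0.03/day | Gap (points) |
|---|---|---|---|---|
| 3 days | 2.9% vs 2.6% | 0.3 | 8.3% vs 7.5% | 0.8 |
| 7 days | 6.5% vs 5.0% | 1.5 | 17.3% vs 13.7% | 3.5 |
| 14 days | 12.2% vs 7.5% | 4.7 | 29.6% vs 19.8% | 9.8 |
| 28 days | 20.9% vs 9.5% | 11.4 | 45.3% vs 24.8% | 20.5 |

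Gaps come from unrounded shares. The simulation assumes that SOC records carry the worst grade reached within Period 1. Section 11.3 does not say so, and if they do not, the gap is larger. These are shares of AEs, not of patients. One patient is 1/16 = 6.25 points of an arm, but an upgraded record moves a patient in the severity table only if it exceeds that patient's other events at the same level.

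**The case against.** First dose of the investigational product is a real change of treatment, and at Day 29 the dasiglucagon-first arm has none. Counting each event once at its worst grade also suits the pooled active-treatment summary in SAP section 9. That explains the anchor, but it does not make the Period 1 columns comparable. Record linkage can serve both purposes.

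The path is narrow: the AE must be unresolved at Week 5 and worsen afterwards. Serious upgrades must be reported within 24 hours and serious TEAEs are listed, so with at most 32 patients they can be checked case by case. The AE content list in Protocol 11.2 is expressly a minimum, and the data entry guidelines are not available here, so dates of grade change may be collected. All of this stands, and it limits how much the problem matters.

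Three stronger readings are tempting and not supported:

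- A reader might infer that total Period 1 TEAEs are inflated. The main path alters grade or seriousness only. Only the screening-onset path could add TEAEs.
- A reader might infer that a screening-onset AE worsening on SOC can never be a TEAE. Section 11.3 is silent on SOC worsening before first dose, and Protocol 11.1.1 treats clinically significant worsening of a concomitant illness as an AE in either arm. What remains uncertain is an AE that begins between consent and Day 1.
- A reader might infer that a formal comparison is compromised. Protocol 12.4.4 and SAP section 9 plan no inferential safety analysis unless otherwise noted.

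**Conclusion.** The main path follows from the text. For an AE that starts in Period 1, is open at Week 5 and then worsens, the Period 1 record carries the later, worse grade on dasiglucagon and the earlier grade on SOC. The SAP does not correct for this. The Period 1 severity and SAE tables can therefore be tilted against dasiglucagon, provided AEs are assigned to periods by onset, which the SAP implies but does not state. The screening-onset asymmetry is secondary and less certain.

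The size is unknown. Under the assumed processes it runs from 0.3 points when AEs last 3 days on average, through roughly 5 to 10 points at 14 days, to more than that only when AEs last as long as the period itself. It may well be small. The direction is against the drug, so harm in Period 1 is not hidden, and no test or error rate is involved. It is worth correcting because it is an arm-dependent artefact in the only randomized safety comparison and the remedy is cheap.

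**What to change.** In Protocol 11.3 and German 12.3, apply the rule from the same two dates in both arms: Day 1 as defined in SAP 6.1.7, and the start of Treatment Period 2 (Visit 5). Record any worsening in severity or seriousness after either date as a separate AE dated at the upgrade and linked to its parent record, and keep worst-case severity within a period. Carry the wording into the eCRF completion guidelines.

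In the SAP, state that AEs are assigned to periods by onset, and merge linked records in the pooled dasiglucagon summary so that an event counts once at its worst grade.

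With the same dates in both arms, the artificial difference is zero by construction on both paths. The cost is wording, slightly more AE records and one linkage rule. For any AEs already recorded under the present rule, those open at Visit 5 would need to be checked against source.
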